#### 4.1.1 Sensitivity analyses of the primary objective

The following sensitivity analyses will be performed: (i) per-protocol, which will include and compare only participants who initiated and completed the regimen to which they were randomized according to the protocol (ie. completed study treatment or discontinued due to death or toxicity); and (ii) as-treated, which will compare participants according to the actual treatment received (ie. participants in the deferred arm who started INH in the antepartum period will be analyzed in the immediate arm).

Sensitivity analyses will be done to assess the impact of coding deaths of unknown cause and all deaths as events. Supplementary analyses will include estimation of the difference in primary endpoint rates between the two arms based on simple estimates of proportions stratified by gestational age, where endpoints will be assessed based on available data (i.e. if participant discontinued the study early and did not experience an endpoint up until that point, then assume no endpoint was reached). Un-weighted (i.e., ignoring stratification by gestational age) estimates for the difference in rates will also be reported.

Multivariable analyses to adjust for maternal characteristics such as treatment arm, age, duration on HAART, CD4 count, gestational age at study entry, IGRA positivity at study entry in all women, and other potential confounders such as HBsAg serology status at entry will be performed using Poisson regression modeling.

Finally, similar analyses will be performed on all Grade  $\geq 3$  AEs (regardless of INH/Placebo for INH attribution) as a way to check for bias in the primary endpoint analysis.

#### 4.2 Analysis of Secondary Objectives

Maternal TB, maternal death, infant TB and infant death will be analyzed separately and as combined events. Efficacy of INH will be assessed primarily by comparing event rates between women in the immediate and deferred arms by 48 weeks postpartum.

A 95% confidence interval for the absolute difference in event rates will be computed using study entry gestational age-stratified Mantel-Haenszel estimates. Unweighted (i.e., ignoring stratification) estimates for the difference in rates will also be reported.

Strategies for censoring will vary depending on the efficacy outcome of interest. For analyses of maternal TB, any maternal death not caused by TB will not be considered an event and any maternal death of unknown cause will be considered an event. Similarly, for analyses of infant TB, any infant death not caused by TB will not be considered an event and any infant death of unknown cause will be considered an event. Sensitivity analysis to assess the effect of this strategy includes coding death due to unknown cause as a non-event.

This will be a modified intent-to-treat analysis, with participants analyzed according to randomized study arm, excluding those who were determined to have active TB at entry.

For final analyses, supplementary analyses will include estimation of differences in these individual/combined endpoint rates between the two arms based on simple estimates for proportions.

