### **3.2 Secondary Endpoints**

- ***In utero* exposure and infant endpoints:**
  - Fetal death
  - Small for gestational age
  - Premature birth (< 37 weeks gestation)
  - Low birth weight (< 2500 gm)
  - Congenital anomalies
  - Grade 3 or higher clinical or laboratory AEs
    - ◆ all AEs
    - ◆ possibly, probably, or definitely related to INH/Placebo for INH
  - HIV infection
  - Hospitalization
- **Any of the following endpoints:**
  - Maternal TB (probable or confirmed – see Appendix 100 for definitions)
  - Infant TB (probable or confirmed, as defined in Appendix 100, and congenital TB, as defined using the Cantwell criteria)
  - Death of infant
  - Death of mother
  - Combined endpoint of maternal TB or maternal death
  - Combined endpoint of infant TB or infant death
  - Combined endpoint of maternal TB, maternal death, infant TB, or infant death

NOTE: TB endpoints and infant cause of death will be reviewed by a Secondary Endpoint Review Committee (SERC), which consists of maternal and pediatric TB specialists who may be

members of the study team. Refer to the Endpoint Review Process document for details of the review process. Appendix 100 will be the basis for adjudication of the TB endpoint by the SERC and is available in the CRF Appendix Codes section of the Frontier Science IMPAACT Portal; the web link to portal can be found in the MOP. Cantwell criteria for Congenital TB are in the MOP and will be collected on the P1078 CRF.

Deaths of enrolled women will receive external review by the IERC for adjudication of study treatment attribution and will also be reviewed by the SERC. The SERC will consider if the cause of death (COD) is due to unrecognized active TB (expected to be rare), from a known cause other than active TB, or from an unknown cause.

- **Occurrence of each of the following safety outcomes in HIV-infected women: during pregnancy up to: (i) delivery (antenpartum) and (ii) 12 weeks postpartum**
  - Grade  $\geq$  3 AEs possibly, probably, or definitely related to INH/Placebo for INH or permanent discontinuation of INH/Placebo for INH due to an adverse event
  - Grade  $\geq$  3 AEs (all-cause)
  - Hepatotoxicity possibly, probably, or definitely related to INH/Placebo for INH
  - Hepatotoxicity (all-cause)

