## **5.11 Maternal and Infant TB**

Validation: The analysis programs in this section will be validated, but not double-programmed.

Note: Mother-infant pairs will be excluded if the mother had TB diagnosis at study entry.

- Listing of active TB events, including blinded ID, treatment arm, event week, site diagnosis, SERC decision, event grade and INH resistance testing results (if available), shown separately for mothers and infants
- Table of SERC-assessed TB and death endpoints: number (%) by arm of the following:
  - Maternal TB cases by type (PULMONARY: 220021-CONFIRMED, 220022-PROBABLE; EXTRAPULMONARY: 220031-CONFIRMED, 220032-PROBABLE)
  - Infant TB cases by type (PULMONARY: 220021-CONFIRMED, 220022-PROBABLE, POSSIBLE; EXTRAPULMONARY: 220031-CONFIRMED, 220032-PROBABLE; CONGENITAL TB).
  - Death of infant
  - Death of mother
  - Maternal TB or maternal death
  - Infant TB or infant death
  - Maternal TB, maternal death, infant TB, or infant death

As event numbers warrant:

- Table of intent-to-treat analysis of difference in endpoint rates between arms, based on stratified Mantel-Haenszel estimates at week 48 postpartum (primary) and simple proportions (sensitivity), stratified by gestational age, for the following endpoints:
  - Maternal TB
  - Infant TB
  - Death of infant
  - Death of mother
  - Maternal TB or maternal death
  - Infant TB or infant death
  - Maternal TB, maternal death, infant TB, or infant death
- Kaplan-Meier plot of time to endpoint from randomization date by study arm and by gestational age, with number of events and number at risk for the following endpoints:
  - Maternal TB
  - Infant TB
  - Death of infant

- Death of mother
- Maternal TB or maternal death
- Infant TB or infant death
- Maternal TB, maternal death, infant TB, or infant death

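### Do the TB endpoints change meaning between SAP Sections 3.2, 4.2 and 5.11 in a way that needs a change to the plan?

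*SAP*

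**What the plan says.** **Case definition (SAP 3.2).** Maternal TB means probable or confirmed disease. For infants the text reads "Infant TB (probable or confirmed, as defined in Appendix 100, and congenital TB", the congenital form being judged by a separate set of criteria. Deaths are not part of either definition. The same section gives the SERC the review of TB endpoints and of infant cause of death. For women it adds "The SERC will consider if the cause of death (COD) is due to unrecognized active TB (expected to be rare"), or else a known cause other than TB, or an unknown cause.

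**Analysis rule (SAP 4.2).** In the maternal TB analysis "any maternal death of unknown cause will be considered an event", and in the infant TB analysis "any infant death of unknown cause will be considered an event". Deaths known not to be from TB are non-events. The section adds "Sensitivity analysis to assess the effect of this strategy includes coding death due to unknown cause as a non-event". On censoring it says only "Strategies for censoring will vary depending on the efficacy outcome of interest".

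**Outputs (SAP 5.11).** One item is the "Table of SERC-assessed TB and death endpoints: number (%) by arm of the following". Its infant line begins "Infant TB cases by type (PULMONARY: 220021-CONFIRMED, 220022-PROBABLE, POSSIBLE" and continues with extrapulmonary and congenital disease. Rate differences and Kaplan-Meier plots follow if there are enough events, under the bare names of the endpoints. Section 5.13 separately tabulates deaths and TB diagnoses learnt after a participant was last seen on study.

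**The concern.** Read quickly, these sections give Infant TB three different contents: cases only in 3.2, cases plus unexplained deaths in 4.2, and cases including possible pulmonary disease in 5.11. Maternal TB has two, since only the deaths differ.

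Other gaps seem to add to this:

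- Section 4.2 counts any unexplained death but does not say whether one reported by a neighbour after loss to follow-up is included.
- Section 4.2 gives no censoring time, whereas 4.1 sets out four censoring rules for the primary endpoint.
- Section 5.11 lists no output for the sensitivity analysis promised in 4.2.
- The death listings in 5.7 and in the infant safety part of 5.10 do not show the SERC's cause-of-death category.

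The stake would be that two analysts report different rate differences under one label. There is also a question of meaning. Secondary objective 1 concerns harm to infants from exposure in utero, so an excess of unexplained early infant deaths could show up under an efficacy heading.

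**Working it through.** The SAP gives no TB rate, unknown-cause death rate or power figure for these endpoints, so there is no stated figure to reproduce. The check is mainly a comparison of texts, with arithmetic to show scale.

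**Step 1: do 3.2 and 4.2 conflict?** Section 3.2 says what a TB case is. Section 4.2 says how deaths are coded in analyses of maternal TB and of infant TB. The rate differences and plots in 5.11 are those analyses, so the 4.2 rule governs them. The maternal case types in 3.2 and 5.11 agree.

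**Step 2: who decides that a cause is unknown?** Section 3.2 gives the SERC this task: for women with unknown cause as one of three named categories, for infants through its review of cause of death. The 5.11 table is also described as SERC-assessed. That the death listings show other sources does not make those sources the input to 4.2.

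**Step 3: does possible TB enter the endpoint?** It appears once, in a count by type, for infant pulmonary disease only and with no diagnosis code. Congenital TB also has no code there, but 3.2 names and defines it. Possible TB is in neither 3.2 nor 4.2, so an analyst following the definition leaves it out of the rate differences and composites.

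**Step 4: whom can the unknown-cause rule affect?** The composites of TB or death already count every death, so the rule changes nobody's status there. It acts only on the TB-alone endpoints, for which 4.2 commits to both codings.

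**Step 5: scale.** Inputs: target 950 women and equal allocation (SAP 1.2), so n = 950/2 = 475 per arm. All event counts below are assumed.

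- One event counted or not in one arm: 1/475 = 0.21 percentage points. For an assumed 490 to 440 infants per arm: 1/490 = 0.20 to 1/440 = 0.23.
- 95% half-width with equal counts x in each arm, unstratified: 1.96 × √(2p(1 − p)/475), p = x/475. This gives 1.01 points for x = 3, 1.30 for x = 5 and 1.83 for x = 10. One event is therefore 0.21/1.30 = 16% of the half-width at x = 5 (21% at x = 3, 12% at x = 10).
- Effect of the death coding itself, starting from 5 v 5 cases: adding unknown-cause deaths of 3 v 1, 5 v 2 or 8 v 3 gives 0.42 (−1.11 to 1.95), 0.63 (−1.05 to 2.32) or 1.05 points (−0.82 to 2.92). These shifts are not small beside the half-width, but they are exactly the contrast between the main and sensitivity codings in 4.2.

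**Step 6: deaths traced after loss to follow-up.** Suppose 10% of each arm is lost: 0.10 × 475 = 47.5. If 1%, 2% or 5% of these are reported dead of unknown cause, the expected extra events per arm are 0.5, 1.0 or 2.4. With two independent binomials of size 48, the chance of an imbalance of two or more (2/475 = 0.42 points) is 0.11, 0.25 or 0.47. The 10% is the threshold in 5.2.1 for drawing extra figures, not a predicted loss rate, and the death fractions are assumed.

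**The case for a change.** The strongest case for a change is that Section 5 of the SAP names Maternal TB and Infant TB as key analyses, yet 5.11 does not require double programming. A wrong reading about possible cases or traced deaths might then go unnoticed. With few events one or two matter, and the remedy would be a few sentences and no new data. Section 1.1 also says that the document details every analysis in the report, and 5.9 lists its own death-coding sensitivity table for the primary endpoint where 5.11 does not.

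What stands is that four details are unwritten: the status of possible infant TB, the censoring time, the handling of events known only from tracing, and an output line for the sensitivity analysis. None makes a stated rule wrong.

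- The programs still undergo code review and execution checks.
- The last detail is a clerical omission, because 4.2 already commits to the analysis.
- For censoring, 4.1 uses the last on-study contact and 5.2.1 measures maternal follow-up to the same point, so the sensible default is at hand.
- Counting traced deaths is a genuine trade-off. Including them recovers some true events, but ascertainment is partial and some reports come from third parties. Excluding them may lose some TB deaths. Section 5.13 reports them either way.

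The worry about early infant deaths is met by other planned outputs. Infant death is an endpoint of its own, deaths within 7 and 28 days of birth are tabulated, and the sensitivity analysis removes unexplained deaths from infant TB. A column showing the SERC's cause of death would help a reader, but it is a reporting preference.

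**Conclusion.** The concern does not call for a change. The apparent shift in numerator between 3.2 and 4.2 is a prespecified death-coding rule with its reverse planned as a sensitivity analysis, and the body that judges cause of death is named. What remains is missing detail that an analyst fills sensibly: use the 3.2 case definition, apply the 4.2 coding in both forms, treat possible infant TB as descriptive, and censor as 4.1 does.

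Each participant whose status depends on the open details moves a rate difference by about 0.21 points. The SAP gives no event rates, so it cannot be shown how many such participants there would be. This rests on 475 per arm and on assumed event counts. The reach is limited to secondary endpoints whose rate differences are run only if there are enough events, and the primary safety comparison does not depend on any of it.

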## 5 Report Components

Notes:

- *Unless otherwise indicated, all outputs will be by treatment arm.*
- *Data presented on individual participants will be identified by Public ID.*
- *Validation requirements per CBAR SOPs:*
  - *All programs that generate permanent study-specific derived datasets that contribute to the generation of reports for final analyses that either contain or are supportive of the analyses of the primary or secondary objectives will be validated; all such programs will undergo code review and execution checks, and the primary safety outcome measures will have results verification (double programming)*
  - *All programs that conduct key analyses for primary or secondary objectives will be validated; all such programs will undergo code review and execution checks, and those programs that conduct the analyses for the primary objective (maternal safety) will have results verification (double programming). The following analyses are considered key: Study/Treatment Status, Study Discontinuation prior to Evaluation of Primary Outcome, Maternal Safety, Infant Safety, Maternal TB, Infant TB. The level of validation required for each of the key analyses is specified below in the respective subsections.*

### 5.1 Accrual

Validation: No validation of the analysis programs is required.

- Table of site activation dates and date of first enrollment
- Table of accrual by month with dates of first and last enrollment will be indicated as a footnote [STATUS]
- Table of accrual by site [STATUS]
- Table of accrual by HAART stratification factor and site [STATUS]
- Table of accrual by gestational age stratification factor and site [STATUS]
- Table of accrual by sub-cohort (intensive PK, PBMC collection, none) and site [STATUS]

### 5.2 Study Status

Validation: The analysis programs for Study Status and Premature Study Discontinuation will be validated, but not double-programmed.

### **5.2.1 Maternal**

- CONSORT diagram, including number of women randomized to each treatment arm (reasons not randomized), number who initiated study treatment (reasons not initiated), and number who completed study (reasons not completed). [STATUS]
- Listing of participants with eligibility violations, including blinded ID, treatment arm, and description of violation [STATUS]
- Table of stratification errors: number (%) by strata [STATUS]
- Table of off-study reasons: number (%) [F1601]
- Table of off-study reasons: number (%) by month and phase of pregnancy (entry to < delivery, delivery to < week 12 PP, week 12 PP to week 48 PP) [F1601]
- Listing of participants not initiating randomized treatment, including blinded ID, treatment arm, and reason [ADM0021]
- Listing of participants who initiated randomized treatment more than 3 days after study entry, including blinded ID, treatment arm, and day of initiation [ADM0021]
- Duration of follow-up defined as time (weeks) from randomization date to last clinic visit (or last contact) while on study: mean (s.d.), min, max, median (Q1-Q3). [STATUS, F1601]
- If more than 10% of participants prematurely discontinue the study, generate the following:
  - Figure of time-to-last clinic visit from randomization date, with comparison by treatment group using log rank test. [STATUS, F0010]
  - Figure of time-to-last clinic visit from randomization date by gestational age stratum with comparison by treatment group using log rank test. [STATUS, F0010]

### **5.2.2 Infant**

- Table of deliveries: number (%) by month [STATUS, EVW0292]
- Table of off-study reasons: number (%) [F1601]

## **5.3 Maternal Baseline Characteristics**

Validation: No validation of the analysis programs is required.

### **5.3.1 Demographics**

- Age (years): N, N missing, mean (s.d.), min, max, median (Q1-Q3); number (%) by age group (eg. <24, 24-<29, 29-<34,  $\geq$ 34) with years rounded down [STATUS]
- Self-reported race/ethnicity: number (%) by category [STATUS]
- Country: number (%) [STATUS]
- Gestational age (weeks) at entry: N, N missing, mean (s.d.), min, max, median (Q1-Q3); number (%) by category (14-<24, 24-34) [OBW0006]
  - Note: Gestational age is determined based on best available method, with methods prioritized as (i) ultrasound, (ii) last menstrual period, (iii) fundal height, and may

not match the level used for stratification if the site defined best available method differently.

### **5.3.2 Health Status**

- Entry HIV-1 RNA (copies/ml): Number (%) by category (eg. <50 cp/ml, 50-<200 cp/ml,  $\geq$ 200 cp/ml) and detectable vs. undetectable (<LLQ). Note: HIV-1 RNA is performed by a “licensed assay” so the limit of quantification could differ by assay type. [RNALDMS]
- Screening CD4 counts (cells/uL): N, N missing, mean (s.d.), min, max, median (Q1-Q3); number (%) by category (eg. <350, 350-<500, 500-<650,  $\geq$ 650) [LBW0054]Entry weight (kg): N, N missing, mean (s.d.), min, max, median (Q1-Q3) [F0031]
- Entry BMI ( $\text{kg}/\text{m}^2$ ): N, N missing, mean (s.d.), min, max, median (Q1-Q3) [F0031, EVW0247]
  - $BMI = (\text{weight}/(\text{height}^* \text{height}/10000))$
- Entry WHO clinical staging for HIV: Number (%) by clinical stage (I, II, III, IV) [PE0043]
- Prior TB treatment (>30 days): number (%) by response (yes, no, unknown) [HXW0166]
- Entry IGRA positivity: Number (%) by status (positive, negative, indeterminate) [TBW0060]
- Entry HBsAg serology: Number (%) by status (positive, negative, indeterminate) [SRW0026]
- Entry hepatitis C serology: Number (%) by status (positive, negative, indeterminate) [SRW0026]

### **5.3.3 Antiretroviral (ARV) Regimen**

- Entry ARV regimen: number (%) by HAART category (HAART, not on HAART) and by actual regimen [PE0412]
- Efavirenz-containing ARV regimen at entry: number (%) by EFV use (yes, no) [PE0412]

### **5.3.4 Laboratory Values**

- ALT: number (%) by grade; mean (s.d.), min, max, median (Q1-Q3)
- AST: number (%) by grade [PE6817]
- Total Bilirubin: number (%) by grade [PE6817]
- ANC (cells/ $\text{mm}^3$ ): number (%) by grade [PE6812]
- Hemoglobin (g/dL): number (%) by grade [PE6812]
- Platelet count (cells/ $\text{mm}^3$ ): number (%) by grade [PE6812]

Note: Grading will be based on Appendix III of protocol for ALT, AST and total bilirubin and by DAIDS Version 1.0 toxicity grade otherwise. Baseline laboratory evaluations were done at screening, except for ALT, which was done at screening and entry. Baseline ALT is calculated as the mean of screening and entry values if both are available.

## 5.4 Maternal Safety

Validation: The analysis programs in this section will be validated, but not double-programmed.

- Tables of new grade 3 or 4 labs and signs/symptoms: number (%) by SOC and grade. [STATUS, PE6812, PE6817, PE6832]
- Table of new grade 3 or 4 diagnoses: number (%) by MedDRA code [EVENTS].
- Table of new grade 3 or 4 primary adverse events (labs, signs/symptoms, and diagnoses): number (%) by MedDRA code [EVENTS]
- Table of serious adverse events (SAEs): number (%) by MedDRA code [EVENTS]

Note: The highest grade experienced by a given participant for each safety event is included.

## 5.5 Maternal Hepatotoxicity

Validation: The analysis programs in this section will be validated, but not double-programmed.

- Table of grade 1, 2, 3, and 4 LFTs (ALT, AST, TBIL): number (%) by highest grade [PE6817]
- Table of hepatotoxicity by type, assuming protocol grading and DAIDS grading, separately: number (%) with Fisher's exact tests with mid-*p* adjustment (Lydersen et al, 2009, *Statistics in Medicine*) [PE6817]:
  - Grade 3 ALT (highest grade)
  - Grade 4 ALT (highest grade)
  - Grade 3 ALT, AST, or TBIL (highest grade)
  - Grade 4 ALT, AST, or TBIL (highest grade)
  - Grade  $\geq 2$  ALT and grade  $\geq 2$  TBIL
  - Grade  $\geq 2$  ALT with symptomatic clinical hepatitis
  - Any hepatotoxicity (defined as any of the above)

Note: Symptomatic clinical hepatitis will be identified based on blinded review (pooled over study arms) by selected protocol team members (at end of study follow-up and prior to data freezing for final analysis). Substitute direct bilirubin for TBIL for participants on atazanavir.

- Create the following by treatment arm and efavirenz use at entry, separately [PE6817, ADM0040]:
  - Peak ALT: min, max, mean (SD), median (Q1-Q3), Wilcoxon rank sum test
  - Table of participant ALT levels (U/L) at scheduled study visits by stage of pregnancy (weeks AP/PP): N, mean (s.d.), median (Q1-Q3)
  - Table with number (%) of participants by ALT grade at scheduled study visits and stage of pregnancy (weeks AP/PP)

- Plot of median (Q1,Q3) ALT level at scheduled study visits by stage of pregnancy (weeks AP/PP)
- Table of estimates (with 95% confidence intervals) of difference in incidence rates between arms, based on stratified Mantel-Haenszel estimates (primary) and simple proportions (sensitivity) at week 48 postpartum, for the following endpoints [STATUS,PE4005,TRAC]:
  - Any hepatotoxicity, possibly, probably, or definitely related to study treatment
  - Any hepatotoxicity, all cause
- Kaplan-Meier plot of time to endpoint from randomization date by study arm and by gestational age, with number of events and number at risk for the following endpoints
  - Any hepatotoxicity, possibly, probably, or definitely related to study treatment
  - Any hepatotoxicity, all cause
- Table of analysis of difference in endpoint rates between arms up to (i) delivery and (ii) 12 weeks postpartum, based on stratified Mantel-Haenszel estimates (primary) and simple proportions (sensitivity), for the following endpoints [STATUS,PE4005,TRAC]:
  - Any hepatotoxicity, possibly, probably, or definitely related to study treatment
  - Any hepatotoxicity, all cause

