Note: Each of the definitions of hepatotoxicity will be studied: (i) having  $\geq$  Grade 3 LFTs (ALT  $> 5 \times$  ULN or ALT  $> 3 \times$  ULN with bilirubin  $> 2 \times$  ULN) or ALT  $> 3 \times$  ULN with persistent, symptomatic clinical hepatitis); and (ii) using DAIDS AE grading criteria, Version 1.0.

- **Resistance outcomes:**
  - Resistance to INH in isolates of *M.tb* from mothers who develop culture-confirmed TB
  - Resistance to INH in isolates of *M.tb* from infants who develop culture-confirmed TB

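### In the section 5.5 by-type table, two tested Grade 3 rows count women who peaked at Grade 4 as non-cases, so those two tests can favour the arm with more severe cases (minor point, cheap fix)

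*SAP*

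**What the plan says.** SAP section 5.5 specifies "Table of hepatotoxicity by type, assuming protocol grading and DAIDS grading, separately: number (%) with Fisher's exact tests", with a mid-p adjustment. The table has seven rows:

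- two for ALT alone: "Grade 3 ALT (highest grade") and "Grade 4 ALT (highest grade");
- two across the three liver tests: "Grade 3 ALT, AST, or TBIL (highest grade") and "Grade 4 ALT, AST, or TBIL (highest grade");
- two that combine ALT of Grade 2 or above with another criterion (bilirubin of Grade 2 or above, or symptomatic clinical hepatitis);
- a union row, "Any hepatotoxicity (defined as any of the above").

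The note in section 5.4 explains highest grade: each woman is entered for each safety event at the worst grade she reached. Nothing in section 5.5 removes Grade 4 women from the denominator of the Grade 3 rows.

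The first bullet of section 5.5 already gives liver test counts by highest grade, with no test. Later bullets give peak ALT by arm with a Wilcoxon rank sum test, stratified Mantel-Haenszel differences at week 48, Kaplan-Meier plots, and Mantel-Haenszel differences up to delivery and up to 12 weeks postpartum. The Mantel-Haenszel and Kaplan-Meier outputs all use any hepatotoxicity, related or all-cause.

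The note in section 3.2 states that "Each of the definitions of hepatotoxicity will be studied". The first of these is a composite built on liver tests of Grade 3 or above.

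**The concern.** A count by highest grade is a sound description, but it makes a poor binary outcome for a test. In the Grade 3 row, the women with the worst liver injury are grouped with women who had none. If some women in one arm move from Grade 3 to Grade 4, that arm's Grade 3 count falls and its row looks better, although its toxicity is worse. The p-value printed beside the row can then point the wrong way and can be quoted alone.

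The natural comparison, Grade 3 or higher, is tested neither for ALT alone nor for the three liver tests together. The only row that pools Grades 3 and 4 is the union row, which also brings in the two combination criteria. The table is not uniform either: its two combination rows do use at-or-above thresholds.

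Hepatotoxicity is named in secondary objective 3, so these p-values will be read. At stake is the interpretation of two rows under each of two gradings, which is four printed tests.

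**Working it through.** **No plan figure to reproduce.** The SAP states no hepatotoxicity rate, power or alpha for these tests. All counts and rates below are assumptions, and two-sided 0.05 is assumed.

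**Inputs.** The target is 950 women randomized in equal proportions (section 1.2), so 950 / 2 = 475 per arm. Call the arms A and B.

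**Formula.** For a row with *a* cases in A and *b* in B, condition on *m = a + b*. The count in A is hypergeometric (950 women, *m* cases, 475 drawn). Let *p0* be the probability of the observed table, *L* the total probability of all less likely tables, and *E* the total probability of all equally likely tables, including the observed one. The Fisher p is *L + E*. With equal arms the mirror table is equally likely, so *E = 2 p0* here, and two mid-p conventions differ:

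- halve the observed table only: *L + E − p0/2*;
- halve all equally likely tables: *L + E/2*.

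**Illustration: A has 4 women peaking at Grade 3 and 16 at Grade 4; B has 13 and 3.**

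| Row | A v B | p0 | L | E | Mid-p, observed halved | Mid-p, all halved | Direction |
|---|---|---|---|---|---|---|---|
| Grade 3 (highest) | 4 v 13 | 0.0175 | 0.0120 | 0.0351 | 0.0120 + 0.0351 − 0.0088 = 0.038 | 0.0120 + 0.0175 = 0.030 | favours A |
| Grade 4 (highest) | 16 v 3 | 0.0017 | 0.0007 | 0.0034 | 0.003 | 0.002 | against A |
| Grade 3 or higher | 20 v 16 | 0.107 | 0.396 | 0.215 | 0.56 | 0.50 | no clear difference |

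The Grade 3 row is nominally significant in favour of A under either convention. Yet A has more women at Grade 3 or higher (4 + 16 = 20 v 13 + 3 = 16) and far more at Grade 4. The cumulative row removes the false advantage.

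A sparser case behaves the same way. With peak Grade 3 of 0 v 5 and Grade 4 of 6 v 0, the Grade 3 row gives mid-p 0.031 to 0.046 in favour of the arm with every Grade 4 case.

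**How often could this happen?** The table shows 40,000 simulated trials per scenario, 475 per arm, observed-table convention. Rates are peak Grade 3 / peak Grade 4.

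| Assumed rates, A v B | Grade 3 row significantly favours A | Grade 4 row significant against A |
|---|---|---|
| No difference: 2%/2% v 2%/2% | 1.8% | 1.7% |
| A worse in both grades: 3%/3% v 2%/1% | 0.1% | 55% |
| Only Grade 4 raised: 2%/3% v 2%/1% | 1.7% | 55% |
| Shift: 1%/3% v 2%/1% | 18% | 55% |
| Shift: 1.5%/3.5% v 3%/1% | 29% | 71% |
| Shift: 1%/5% v 3%/1% | 55% | 96% |
| Shift: 0.8%/3.4% v 2.7%/0.6% | 56% | 87% |

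In the four shift scenarios, the Grade 3 row favours A with neither the Grade 4 row nor a Grade 3 or higher test significant against A in only 2% to 8% of trials.

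**The case against.** The strongest reply is that the rest of section 5.5 already protects the reader. A Grade 4 row sits directly beneath each Grade 3 row, and the union row counts both grades as cases. The Wilcoxon test on peak ALT responds to severity, since a move from Grade 3 to Grade 4 raises ranks in the worse arm. The between-arm estimates for objective 3 are Mantel-Haenszel differences on any hepatotoxicity, which cannot reverse in this way. Cumulative counts can be had by adding two adjacent rows, and highest-grade tabulation is the SAP's usual reporting style. All of this stands, and it limits the point to two rows of a supporting table.

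Three stronger readings are tempting, but the SAP does not support them.

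- A reader might infer that the hepatotoxicity tests in general can point the wrong way. Only two of the seven rows under each grading can.
- A reader might infer that section 3.2 is breached because no single-analyte row tests Grade 3 or higher. Section 3.2 gives a composite definition, which the union row broadly serves, and it promises no single-analyte test.
- A reader might infer that a more toxic arm is likely to look safer. If an arm is worse in both grades, or in Grade 4 only, a significant wrong-direction Grade 3 result is no more frequent than under no difference. It takes a fall in Grade 3 together with a rise in Grade 4, and the SAP gives no rates that suggest such a pattern.

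The reply does not explain why a p-value should be attached to the exclusive Grade 3 rows at all.

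**Conclusion.** The point holds in a narrow form. Two of seven tested rows, under each of two gradings, treat Grade 4 women as non-cases. Those tests are not monotone in toxicity, and a nominally significant result in favour of the arm with more severe cases is possible, as the 4 v 13 illustration shows under both mid-p conventions.

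The conclusion rests on reading highest grade literally, as section 5.4 uses it, and on no unstated rule that drops Grade 4 women from the denominator. The sizes rest on assumed counts and rates, 475 women per arm and a two-sided 0.05 level; how likely a reversal is in this trial cannot be settled from the SAP. This is a cheap improvement to a supporting table and does not threaten the main hepatotoxicity analyses.

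**What to change.** In the section 5.5 by-type table, replace the two tested Grade 3 rows with Grade 3 or higher ALT, and Grade 3 or higher ALT, AST or total bilirubin. Keep both Grade 4 rows with their tests. Leave counts by highest grade as description without tests, as the first bullet of section 5.5 already does.

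The any-hepatotoxicity union contains the same women before and after the change, so the Mantel-Haenszel and Kaplan-Meier outputs do not move. The cost is a small change to SAP wording and to the table program, with the code review and execution checks that section 5 already requires.
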